### 5.7.1.3. PK vs Efficacy

To explore the relationship between JNJ-77242113 plasma concentrations and efficacy endpoints, the following analyses may be explored:

- The relationship between JNJ-77242113 plasma concentrations (quartiles) and PASI 75 response and IGA 0/1 response at Week 16 may be explored.

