### 3. OBJECTIVES AND ENDPOINTS

Objectives	Endpoints
Primary	

 
To evaluate the efficacy of an oral tablet formulation of JNJ-77242113 compared with placebo in participants with moderate-to-severe plaque psoriasis.
 
	
 
Proportion of participants achieving Psoriasis Area and Severity Index (PASI) 75 (<math>\geq 75\%</math> improvement in PASI) at Week 16.
 

Secondary	

 
To assess the safety and tolerability of an oral tablet formulation of JNJ-77242113 compared with placebo in participants with moderate-to-severe plaque psoriasis.
 
	
 
Frequency and type of adverse events (AEs) and serious adverse events (SAEs).
 

 
To evaluate additional measures of efficacy of an oral tablet formulation of JNJ-77242113 compared with placebo in participants with moderate-to-severe plaque psoriasis.
 
	
 
Change from baseline in PASI total score at Week 16.
 
Proportion of participants achieving PASI 90 (<math>\geq 90\%</math> improvement from baseline in PASI) at Week 16.
 
Proportion of participants achieving PASI 100 (100% improvement from baseline in PASI) at Week 16.
 
Proportion of participants achieving an Investigator Global Assessment (IGA) score of cleared (0) or minimal (1) at Week 16.
 
Proportion of participants achieving an IGA score of cleared (0) at Week 16.
 
Change from baseline in body surface area (BSA) at Week 16.
 

Exploratory	

 
To characterize the pharmacokinetics (PK) of JNJ-77242113 for the oral tablet formulation and explore the PK/pharmacodynamic (PD) relationship of the JNJ-77242113 formulation for
 
	
 
JNJ-77242113 PK parameters (ie, plasma concentration just prior to the beginning or at the end of a dosing interval [<math>C_{trough}</math>], area
 

Objectives	Endpoints
biomarkers, efficacy, and safety in participants with moderate-to-severe plaque psoriasis.	
under the plasma concentration versus time curve [AUC]).
 
 
The relationship between PK parameters and PD (ie, skin, blood cellular and molecular biomarker activity as well as clinical endpoints and safety parameters).
 

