### **Pharmacokinetic/Pharmacodynamic Analyses**

If data permit, the relationships between plasma JNJ-77242113 concentration and efficacy may be examined when appropriate. If a relationship is observed, a suitable PK/PD model may be developed to describe the exposure-response relationship and will be presented in a separate technical report.

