## 3. SAMPLE SIZE DETERMINATION

This study is designed to assess the clinical response, safety/tolerability, and pharmacology of JNJ-77242113 CCI in participants with moderate-to-severe plaque psoriasis. The sample size is evaluated based on the primary endpoint of a PASI 75 response at Week 16. The sample size of 80 participants was chosen in order to have sufficient power to detect a difference between the JNJ-77242113 CCI (30 participants for each of low and high dose groups) and the placebo group (20 participants).

The assumptions for the sample size and power calculations were mainly based on the clinical data from guselkumab Phase 3 clinical studies that evaluated the safety and efficacy in the treatment of adult participants with moderate-to-severe plaque psoriasis.

The null hypothesis is to be tested at an overall Type 1 error rate of 0.10 (2-sided). Assuming PASI75 response rates at Week 16 are 5% to 10% for placebo and 40% to 80% for JNJ-77242113 CCI, a sample size of 20 participants in the placebo group and 30 participants in the JNJ-77242113 CCI will provide at least 90% power to detect a 35% difference between the JNJ-77242113 CCI and placebo groups in the proportion of participants achieving a PASI 75 response at Week 16 based on a 2-sample Z-test.

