#### **5.7.3. Pharmacokinetic/Pharmacodynamic Relationships**

The relationship between plasma concentration of JNJ-77242113 and PD may be analyzed graphically. If any visual trend is observed, a suitable PK/PD model may be developed to describe the exposure-response relationship. In the latter case, the results of the PK/PD modeling analysis will be presented in a separate technical report.

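### The only exposure-efficacy analysis with named variables categorises both concentration and response; a continuous model on data already collected would use more of the information

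*SAP*

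**What the plan says.** Protocol section 3 and SAP 1.1 make the PK/PD relationship, for efficacy among other things, an exploratory objective. The matching endpoint begins "The relationship between PK parameters and PD" and counts clinical endpoints within PD.

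SAP 5.7.1.3 gives the analysis: "The relationship between JNJ-77242113 plasma concentrations (quartiles) and PASI 75 response and IGA 0/1 response at Week 16 may be explored". It does not name a test, a model, an exposure metric or a concentration visit, and it does not say whether the quartiles are pooled across doses or formed within dose.

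Two other places bear on the question:
- SAP 5.7.3 allows concentration to be plotted against PD, and then: "If any visual trend is observed, a suitable PK/PD model may be developed".
- Protocol 9.4.6 allows concentration to be examined against efficacy if the data permit, and then: "If a relationship is observed, a suitable PK/PD model may be developed".

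Neither fixes a response scale, an exposure metric or a model form. SAP 5.7.1.1 and 5.7.1.2 set concentrations below the quantification limit to zero in summaries. SAP 5.7.1.2 also drops by-visit data after discontinuation of study agent and after certain dosing deviations.

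**The concern.** Plasma concentration is continuous and so is percent improvement in PASI. The one analysis with both variables named reduces the first to four groups and the second to two, in at most 60 people. A real gradient is harder to see on that scale.

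If the quartiles are pooled, the two doses are five-fold apart, so the lower two quartiles are mostly the 10 mg group and the upper two mostly the 50 mg group. The table then largely repeats the randomised dose comparison and says little about exposure within a dose, which is what an exposure analysis could add.

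At stake is how well an exploratory objective is answered. The primary analysis is not affected.

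**Working it through.** **The plan's own figure.** The documents give no power for the exposure-efficacy analysis. The only power statement (SAP 3) is for the primary endpoint: at least 90% for a 35-point difference, 30 active vs 20 placebo, two-sided 0.10, two-sample Z-test. With unpooled variance, power = Φ(d/SE − 1.645).
- 5% vs 40%: SE = √(0.05×0.95/20 + 0.40×0.60/30) = 0.1019, so Φ(3.436 − 1.645) = 96.3%.
- 10% vs 45%: SE = √(0.10×0.90/20 + 0.45×0.55/30) = 0.1129, so Φ(3.100 − 1.645) = 92.7%.

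The stated figure is reproduced on that form (pooled variance gives 91.8% and 87.6%). It does not carry over to exposure-efficacy.

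**Inputs for the illustration.**
- From SAP 3: "30 participants for each of low and high dose groups", so at most 60 active participants and 60/4 = 15 per pooled quartile; two-sided alpha 0.10; planning assumption "response rates at Week 16 are 5% to 10% for placebo and 40% to 80% for JNJ-77242113".
- Assumed, because the documents give no value: between-participant CV of 50% or 100%; a log-concentration shift of ln 5 = 1.609 between doses (dose-proportional exposure); a latent normal response linear in log concentration; pooled quartiles; a trend test or a 3-df chi-square.

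**Pooled quartiles and dose.** Within-dose SD of log concentration is s = √ln(1+CV²): 0.472 at CV 50%, 0.833 at CV 100%. The midpoint between doses is 1.609/2 = 0.805. The share of 10 mg participants falling below it is Φ(0.805/0.472) = 96% or Φ(0.805/0.833) = 83%. So 83% to 96% of the lower half is 10 mg.

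**Power by simulation** (4,000 runs per cell; CV 50% / CV 100%):

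| PASI 75, 10 mg vs 50 mg | Quartile chi-square, 3 df | Quartile trend | Both continuous | Trend loss (points) |
|---|---|---|---|---|
| 40% vs 60% | 38 / 53% | 52 / 68% | 73 / 89% | 21 / 21 |
| 60% vs 80% | 43 / 58% | 60 / 76% | 83 / 95% | 23 / 19 |
| 40% vs 80% | 93 / 99% | 98 / 100% | 100 / 100% | 2 / 0 |

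Hand check of one cell (40% vs 60%, CV 50%). The probit difference is 2×0.2533 = 0.507. Solving b×1.609/√(1 + b²×0.223) = 0.507 gives b = 0.318. The SD of log concentration over both doses is √(0.223 + 0.805²) = 0.933. The pooled correlation is 0.318×0.933/√(1 + (0.318×0.933)²) = 0.285. Power ≈ Φ(atanh(0.285)×√57 − 1.645) = 71%, against 73% simulated.

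**Second parameterisation** (n = 60, correlation 0.2 to 0.5 between log concentration and response, response rates 40, 60 and 80%, 2,000 runs per cell):
- At correlation 0.3 and 60% response, power is about 77% with both variables continuous, 53–54% with the quartile trend test and 38–39% with the 3-df chi-square.
- The trend-test loss is 14–24 points for correlations 0.2–0.4 at 40–60% response, 5–9 points at 0.5 for those rates, and 16–34 points at 80% response.

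Over both sets of scenarios the loss is about 0 to 34 points.

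**Where the loss arises** (second parameterisation). Quartiles in place of continuous concentration cost about 2–9 points with the binary response kept, and about 0–8 with a continuous response. Making the response binary, with concentration kept continuous, costs about 4–27. The binary response is usually the larger part.

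**Within-dose slope.** The continuous powers above are for the pooled slope, which dose itself also drives. With dose in the model, the correlation for 40% vs 60% at CV 50% is 0.318×0.472/√(1 + (0.318×0.472)²) = 0.149, and power is about Φ(atanh(0.149)×√56 − 1.645) = 30%. Across 40% vs 60% and 60% vs 80%, power is roughly 30–39% at CV 50% and 64–78% at CV 100%.

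**The case against.** The strongest reply is that there is no planned test whose power could be lost. SAP 5.7.1.3 describes one optional summary. The trend test, the chi-square, the CVs and the slopes are the reviewer's, so a single figure such as 20 points cannot be derived from the documents. That stands, and the size is therefore given as a range with its assumptions.

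A reader might infer that the quartile table is the screen for PK/PD modelling, so that a missed trend means the model is never built. The documents do not support this. SAP 5.7.3 ties its model to a visual trend in an uncategorised plot. Protocol 9.4.6 allows concentration against efficacy with no categories. Population PK has its own analysis plan. A reader might also infer that dose selection hangs on this table, but the Week 8 interim is what informs Phase 3, and dose-ranging belongs to the parallel Phase 2b study.

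It is also fair that PASI 75 and IGA 0/1 are the primary and a secondary endpoint, so relating exposure to them is sensible. That supports keeping them, though not as the only response scale.

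Two technical objections stand. Values below quantification are set to zero and cannot be logged, whereas rank-based quartiles cope with them. And percent PASI improvement is capped at 100%, unlike the simulated response; an illustrative cap cost 1–7 points of the continuous method's power.

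**Conclusion.** The point holds as a modest one. SAP 5.7.1.3 is the only exposure-efficacy analysis with named variables, and it categorises both of them in at most 60 participants. If pooled, the quartiles largely restate dose. Against a quartile trend test the illustrative loss is about 0 to 34 points of power: about 20 in mid-range scenarios, near 0 when the slope is steep. This rests on assumed PK variability, slope and response rates and on a test the plan does not name.

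The gain comes mainly from restoring a continuous response. A continuous model will not settle the within-dose question at this sample size, but it would give an estimate and interval where the present text promises neither. Priority is low: nothing in the primary or secondary analyses changes.

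**What to change.** In SAP 5.7.1.3:
- Add a regression of Week 16 percent PASI improvement on log exposure as a continuous variable, using model-derived individual Ctrough or AUC (Protocol 8.4.3) where available.
- If observed concentrations are used instead, name the visit and state a rule for values below quantification, such as a rank-based analysis or a stated substitution other than zero.
- Report the slope with a 90% CI, in line with SAP 5.1, both overall and with dose group in the model. Note in advance that the within-dose slope will be imprecise.
- Add logistic regression of PASI 75 and IGA 0/1 on log exposure as companions.
- Keep the quartile table as a display and a check on linearity, and say whether its quartiles are pooled or within dose.

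PASI and plasma concentration are both already scheduled at Week 16, so no samples or visits are added. The costs are SAP wording, a linearity assumption on the log scale, the below-quantification rule, and one or two extra exploratory models.

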## 5.7.2. Immunogenicity

### 5.7.2.1. Antibodies to JNJ-77242113

Immune response analyses will be based on the Immunogenicity Analysis Set.

The incidence and titers of antibodies to JNJ-77242113 will be summarized for all participants who receive at least 1 dose of JNJ-77242113 and have appropriate samples for detection of antibodies to JNJ-77242113 (ie, participants with at least 1 sample obtained after their first dose of JNJ-77242113).

The antibody to JNJ-77242113 status (positive at any time, negative) and titers will be summarized by treatment group for participants who receive a dose of JNJ-77242113 and have appropriate samples for detection of antibodies to JNJ-77242113 (ie, participants with at least 1 sample obtained after their first dose of JNJ-77242113).

Participants evaluable for immunogenicity are defined as having at least 1 dose of JNJ-77242113 and have at least 1 valid blood sample drawn for antibody detection. The antibodies to JNJ-

77242113 summary and analysis will be based on the observed data; therefore, no imputation of missing data will be performed.

The following analysis of antibodies to JNJ-77242113 will be performed by treatment group:

- Summary of incidence of antibody to JNJ-77242113 status
- Summary of neutralizing antibodies (NAb) to JNJ-77242113

A listing of participants who are positive for antibodies to JNJ-77242113 will be provided. The sample antibody status, the titer, and the neutralizing antibody status to JNJ-77242113 will be listed by visit. This listing will also provide information regarding dose administered, JNJ-77242113 plasma concentration, PASI score, PASI75 response status, and IGA 0/1 response status for all applicable visits. In addition, a list of antibodies to JNJ-77242113 status in participants who discontinued study agent early will be provided.

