
 
To explore treatment effects of an oral tablet formulation of JNJ-77242113 on biomarkers in participants with moderate-to-severe plaque psoriasis.
 
	
 
Change from baseline in levels of skin and blood biomarkers.
 

 
To evaluate the immunogenicity of JNJ-77242113.
 
	
 
The incidence of anti-drug antibodies to JNJ-77242113.
 

 
To further assess the safety and tolerability of an oral tablet formulation of JNJ-77242113 compared with placebo in participants with moderate-to-severe plaque psoriasis.
 
	
 
Frequency and type of AEs, SAEs, reasonably related AEs, and AEs leading to discontinuation of study intervention.
 
Laboratory parameters and change from baseline in laboratory parameters (hematology and chemistry) over time.
 
Systolic and diastolic blood pressures over time.
 

 
To evaluate the treatment effect of an oral tablet formulation of JNJ-77242113 on patient-reported psoriasis severity and dermatology-specific health-related quality of life compared with placebo in participants with moderate-to-severe plaque psoriasis.
 
	
 
Change from baseline in Psoriasis Symptoms and Signs Diary (PSSD) symptoms score at Week 16.
 
Change from baseline in PSSD signs score at Week 16.
 
Proportion of participants achieving a PSSD symptoms score=0 at Week 16 among participants with a baseline symptom score <math>\geq 1</math>.
 
Proportion of participants achieving a PSSD signs score=0 at Week 16 among participants with baseline sign scores <math>\geq 1</math>.
 
Proportion of participants achieving a Dermatological Life Quality Index (DLQI) score of 0 or 1 at Week 16 among participants with baseline DLQI score <math>>1</math>.
 

Refer to Section 8, Study Assessments and Procedures for evaluations related to endpoints.

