### 9.3. Populations for Analysis Sets

For the efficacy analyses in this study, the full analysis set (FAS) will be used according to the participants' assigned treatment to which they were randomized, regardless of the treatment they received. The FAS includes all randomized participants who receive at least 1 administration of study intervention. The FAS will be used for all primary and secondary efficacy analyses.

Safety analyses will include all randomized participants who received at least 1 administration of study intervention and participants will be analyzed based on the treatment they actually received,

regardless of the treatment groups to which they were assigned. Pharmacokinetics analyses for JNJ-77242113 will include all randomized participants who receive at least 1 complete dose of JNJ-77242113 CCI and have at least 1 valid blood sample drawn for PK analysis after their first dose of JNJ-77242113 CCI. Antibodies to JNJ-77242113 will be analyzed for all randomized participants who receive at least 1 dose of JNJ-77242113 CCI and have at least 1 sample obtained after the first dose of JNJ-77242113 CCI for the detection of antibodies to JNJ-77242113.

For purposes of analysis, the following populations are defined:

Population	Description
Enrolled	All participants who sign the ICF.
Randomized	All participants who were randomized in the study.
FAS	All randomized participants who take at least 1 dose of study intervention.
Safety Analysis Set	All randomized participants who take at least 1 dose of study intervention.
PK Analysis Set	All randomized participants who take at least 1 complete dose of study intervention and had at least 1 valid blood sample drawn for PK analysis after their first dose of study intervention.
Immunogenicity Analysis Set	All randomized participants who take at least 1 complete dose of study intervention and had at least 1 sample obtained after their first dose of study intervention.

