**Table 1: Populations for Analyses**

| Population                  | Description   |
|-----------------------------|---|
| Enrolled                    | All participants who signed the ICF   |
| Randomized                  | All participants who were randomized in the study   |
| FAS                         | All randomized participants who took at least 1 dose of study intervention  |
| Per Protocol (PP)           | The per protocol analysis set (PP) includes a subset of participants in the full analysis set (FAS) who were in compliance with the protocol. Compliance is defined as participants in FAS and meet the following criteria: 
 
Has a total BSA <math>\geq 10\%</math> at the screening and baseline visit.
 
Has a total PASI score <math>\geq 12</math> at the screening and baseline visit
 
Has a total IGA score <math>\geq 3</math> at the screening and baseline visit
 
Overall compliance of study treatment at least 80% prior to Week 16, Or participants who did not complete all scheduled study intervention administration due to intercurrent events (i.e., discontinued the study intervention due to lack of efficacy, an AE of worsening of psoriasis, or started a protocol-prohibited medication or therapy during the study that could improve psoriasis)
 
Criteria added as needed after the team's review.
 
 |
| Safety Analysis Set         | All randomized participants who took at least 1 dose of study intervention  |
| PK Analysis Set             | All randomized participants who received at least 1 dose of JNJ-77242113 CCI and had at least 1 valid blood sample drawn for PK analysis after their first dose of JNJ-77242113 CCI   |
| Immunogenicity Analysis Set | All randomized participants who received at least 1 dose of JNJ-77242113 CCI and who had at least 1 sample obtained after the first dose of JNJ-77242113 for the detection of antibodies to JNJ-77242113  |
| PD Analysis Set             | All randomized participants who received at least 1 dose of JNJ-77242113  |

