#### **5.7.2.3. Antibody vs Efficacy/PK**

To explore the relationship between antibodies to JNJ-77242113 status and plasma JNJ-77242113 concentrations, efficacy and safety, the following analysis may be performed as appropriate:

- Summary of clinical response (e.g., PASI75 and IGA 0/1) by antibody to JNJ-77242113 status
- Summary of plasma JNJ-77242113 concentrations by antibody to JNJ-77242113 status
- Plots of median (IQ) plasma JNJ-77242113 concentrations over time by antibody to JNJ-77242113 status

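### Antibody status has no treatment-emergent definition, so reactivity present before the first dose counts in the summarised ADA incidence

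*SAP*

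**What the plan says.** Protocol Section 3 lists an exploratory endpoint: "The incidence of anti-drug antibodies to JNJ-77242113". The Schedule of Activities (Protocol 1.3) places the serum antibody sample at Weeks 0, 2, 4, 8, 16 and 20 and at early termination. Footnote r requires the Week 0 samples to be taken before study drug.

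SAP 5.7.2.1 gives the only status rule: "The antibody to JNJ-77242113 status (positive at any time, negative) and titers will be summarized by treatment group". SAP 5.7.2.2 then summarises neutralising antibodies among participants who are antibody positive. SAP 5.7.2.3 lists analyses that may be done, including "Summary of clinical response (e.g., PASI75 and IGA 0/1) by antibody to JNJ-77242113 status" and concentrations by the same status.

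On who is included, SAP 5.7.2.1 opens with "Immune response analyses will be based on the Immunogenicity Analysis Set". SAP Table 1 (Populations for Analyses) limits that set to recipients of JNJ-77242113 "who had at least 1 sample obtained after the first dose of JNJ-77242113 for the detection of antibodies to JNJ-77242113". Protocol 9.3 likewise requires that participants "had at least 1 sample obtained after their first dose of study intervention". SAP 5.7.2.1 twice repeats the restriction to "participants with at least 1 sample obtained after their first dose of JNJ-77242113", but a later sentence describes evaluable participants as having "at least 1 valid blood sample drawn for antibody detection", with no timing.

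**The concern.** The risk table in Protocol 2.3.1 treats antibodies as something the peptide might induce, with possible loss of efficacy or hypersensitivity. A status that is positive on any sample, including the pre-dose one, does not measure induction. It mixes antibodies that appeared on treatment with reactivity the participant brought to the trial.

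SAP Table 1 restricts the set to recipients of active drug, so the summary has no placebo column from which background reactivity could be judged. The SAP makes the pre-dose/post-dose distinction elsewhere: 5.6.2 defines treatment-emergent adverse events and 5.6.3.2 refers to treatment-emergent abnormal vital signs. The antibody section has no equivalent.

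At stake are the reported incidence, the neutralising-antibody proportion built on it, and any comparison of response or concentration by antibody status. All three rest on what may be a small positive group, where a few participants can change the picture.

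**Working it through.** The plan states no antibody rate, so there is no figure to reproduce. The check is a reading of the rules followed by an illustration on assumed rates.

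**Step 1: which samples set status.** Take a participant reactive at Week 0 and negative at Weeks 2 to 20. Post-dose samples exist, so the participant is in the Immunogenicity Analysis Set. One sample is positive, so the status is positive and the participant counts in the incidence. A participant reactive at every visit with a flat titre also counts. The post-dose requirement decides who is in the set, not which samples decide status, so it prevents neither case.

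**Step 2: where the status goes next.** The denominator in 5.7.2.2 is antibody-positive participants, so those in Step 1 enter it if their samples are evaluable for neutralising antibody. The groups in 5.7.2.3 use antibody status without further definition.

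**Step 3: timing.** SAP 5.7.1.1 stops PK summaries at Week 16. SAP 5.7.2.1 to 5.7.2.3 set no such limit, and samples continue to Week 20, about 4 weeks after the last dose. If 5.7.2.3 is run on Week 16 response, a participant first positive at Week 20 falls in the ADA-positive group for an outcome that came first.

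**Step 4: evaluability.** SAP Table 1, Protocol 9.3 and two sentences of SAP 5.7.2.1 require a post-first-dose sample. One sentence of 5.7.2.1 does not. The analysis set governs, so this is a wording conflict and not the cause of Step 1.

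**Step 5: size.** Inputs: 60 active participants (30 per dose, SAP Section 3). Assumed, not from the documents: *b*, the share reactive at Week 0, 1% to 10%; *t*, the share of Week 0 negatives who convert, 5% to 20%.

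- Any-time positive rate: A = 1 − (1 − b)(1 − t)
- Newly positive rate: N = t(1 − b)
- Share of positives reactive before dosing: S = b / A

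Worked case, b = 10%, t = 5%: A = 1 − 0.90 × 0.95 = 0.145; N = 0.05 × 0.90 = 0.045; S = 0.10 / 0.145 = 69%.

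| b | t | Any-time positives of 60 | Newly positive of 60 | S |
|---|---|---|---|---|
| 1% | 5% | 3.57 (5.95%) | 2.97 | 16.8% |
| 5% | 5% | 5.85 (9.75%) | 2.85 | 51.3% |
| 10% | 5% | 8.70 (14.5%) | 2.70 | 69.0% |
| 1% | 20% | 12.48 (20.8%) | 11.88 | 4.8% |
| 5% | 20% | 14.40 (24.0%) | 11.40 | 20.8% |
| 10% | 20% | 16.80 (28.0%) | 10.80 | 35.7% |

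The gap A − N equals b, which is 0.6 to 6 participants of 60. The chance of at least one pre-dose positive among 60 is 1 − (1 − b)^60: 45% at b = 1%, 95% at 5% and 99.8% at 10%. S counts everyone reactive at Week 0. Any whose titre then rose would be a genuine treatment-boosted response, so S is an upper limit on the misclassified share.

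**The case against.** The strongest reply is that the endpoint is exploratory, descriptive and untested, and that the SAP never calls the incidence drug-induced. For each positive participant, SAP 5.7.2.1 also lists sample status, titre, neutralising status, concentration, PASI 75 and IGA 0/1 by visit. With a handful of positives, a reader could pick out those reactive at Week 0 or first positive at Week 20. This stands as mitigation and keeps the severity low. It does not repair the summary tables, which are what report the incidence.

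One could also argue that status is meant to rest on post-dose samples only. The text does not say so. Even on that reading, a participant reactive at Week 0 and still reactive afterwards with no titre rise would be counted.

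Three stronger readings are tempting and are not supported:

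- *That participants with only a Week 0 sample are analysed as negative and dilute the incidence.* The governing set and the sentences defining the incidence and status summaries all require a post-dose sample, so these participants are excluded. Only one loose sentence says otherwise.
- *That the SAP plans to relate Week 20 antibodies to Week 16 response.* SAP 5.7.2.3 names no response visit and is optional. Week 16 is named in 5.7.1.3, which concerns PK and efficacy. The timing problem is conditional on how the analysis is run.
- *That about two-thirds of positives would be spurious.* That is one corner of an assumed range. With 20% conversion the pre-dose share is 5% to 36%.

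**Conclusion.** The point holds as a minor one. As written, the status rule counts pre-dose reactivity in the ADA incidence and carries it into the neutralising-antibody denominator. It also leaves the optional by-status summaries without an antibody cut-off. The evaluability sentence is a separate inconsistency to tidy up.

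The size is unknown from the documents. The range of about 5% to 69% of positives rests wholly on assumed Week 0 reactivity of 1% to 10% and assumed conversion of 5% to 20% among Week 0 negatives. If no one is reactive at Week 0, the incidence is unaffected. The primary and secondary efficacy analyses are not touched.

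**What to change.** In SAP 5.7.2.1, define treatment-emergent ADA as either negative at Week 0 and positive at any later visit, or positive at Week 0 with a post-dose titre rise above a fold fixed in advance (for example, the assay's minimum significant ratio). Use this for the incidence and state the population for 5.7.2.2 accordingly. Report Week 0 prevalence separately. Reword the evaluability sentence to match SAP Table 1 (Populations for Analyses).

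In SAP 5.7.2.3, if the analysis is run, name the response visit. For Week 16 response and for concentrations through Week 16, use treatment-emergent status up to and including the Week 16 visit. List participants first positive at Week 20 separately.

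The cost is SAP wording and some extra programming, since the Week 0 samples and the titres of confirmed positives (Protocol 8.7) are already planned. The downside is a slightly smaller ADA-positive group.
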